This study will address critical questions about SR interventions (in CCCs and elsewhere), including, for example: 1) Do we need a suicide-specific approach (CAMS) to address SR or is TAU sufficient as a first stage intervention? 2) Do we need an intensive, suicide-focused approach (CC-DBT) for individuals who do not respond to first-stage interventions? 3) Are the costs incurred by a more comprehensive approach (CC-DBT) worth it relative to the gains? We will also be able to determine differential effects of a particular sequence. We may find, for example, that clients are satisfied with CC-DBT after CAMS, but not after TAU (or vice-versa) or that only CC-DBT reduces SR among insufficient responders to stage 1. Few other designs allow this level of contextual understanding. Thus, this methodological approach (ATSSs and a SMART), independent of the context of CCCs, is particularly innovative in terms of its application to SR.

Utilizing CAMS and CC-DBT, Distinct Suicide-Focused Treatments, in a Sequenced Format is Innovative

Examining what theoretically distinct approaches have to offer and then bringing them together in a sequence of care is innovative. CC-DBT might not be needed for all suicidal college students;¹⁰ conversely CAMS, a flexible first-line approach of low intensity and cost, might be all that is needed for many, but not all, suicidal college students.²⁷ As far as we know, this is the first attempt to bring these two distinct suicide-focused approaches, one that is flexible and theoretically agnostic and one that is multimodal and comprehensive, together in an adaptive, pragmatic, and rigorous scientific manner.

Attempting to Improve the Quality of Mental Health Services in CCCs is Innovative

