Aim 7. To explore counselor experiences working with suicidal college students. All analyses for this aim will be exploratory. Counselors will	CSQ-8 (Therapist Version) and Reasons for Termination Checklist	Aspects of counselor participants' experiences to be explored include their beliefs about suicide, self-identified theoretical orientation and training

Table 2. CAMPUS Trial Objectives, Endpoints, and Justification

Objectives	Endpoints	Justification for Endpoints
be separated into clinically relevant groups based on cut-points on key demographic variables. Between-group differences on counselor measures will be explored.	Counselor Treatment Expectations Zero Suicide Workforce Survey (abbreviated) Focused Interview Demographic Information Form TAU Questionnaire	experiences, expectations for and satisfaction with providing different types of therapy during the study, and general experiences of participating in the study.
Aim 8: Within each treatment stage, determine whether CAMS produces greater reductions in SR than TAU (Stage 1) and whether CC-DBT produces greater reductions in SR than Continued CAMS (Stage 2).	Scale for Suicidal Ideation (SSI) Self-Injurious Thoughts and Behaviors Interview (SITBI)	The primary outcomes will be reduction in suicidal risk (SR; suicidal ideation primarily but also non-suicidal self-injury, suicide attempts, and suicides) at the end of Stage 1, Stage 2, and at 3-month follow-up. Recognizing that measurement of suicide-related behaviors is fraught with challenges, ¹¹² we are defining SR as “suicidal ideation, attitudes, behaviors and plans which take into account severity, intent, and ability to cope with ideation without engaging in suicidal behaviors, such as planning/rehearsal, non-suicidal self-injury (NSSI), suicide attempts (SAs), and suicide.” Our primary assessment measures for SR are two interviews to measure suicidal ideation (SI; defined as self-reported thoughts of suicide-related behavior) and suicidal behaviors, including suicide attempts and NSSI. Suicides will also be tallied.

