4.2 OVERALL DESIGN

As shown in Figure 1 (on page 9), the proposed multisite SMART will involve randomization at two stages. At Stage 1, all student participants ($N = 480$) will be randomized to 4-6 weeks of CAMS or TAU. Beginning at session 4, the counselor will rate the student participant in terms of clinical response. Insufficient responders (e.g., non-responders) to Stage 1 will be re-randomized to one of two Stage 2 treatments for an additional 1-8 weeks: 1) CAMS (either continued or for the first time) or 2) CC-DBT.

Thus, four ATSSs are possible:

- ATS-1: Start with CAMS, if responding, enter maintenance treatment; if not, continue with CAMS;
- ATS-2: Start with CAMS, if responding, enter maintenance treatment; if not, switch to CC-DBT;
- ATS-3: Start with TAU, if responding, enter maintenance treatment; if not, switch to CAMS;
- ATS-4: Start with TAU, if responding, enter maintenance treatment; if not, switch to CC-DBT.

Our pilot showed at Stage 1, 48% and 44% treatment response rates across CAMS and TAU, with 27% and 17% attrition rates, respectively—differences not statistically significant. Based on these findings, we assume an equal response rate of 50% across both Stage 1 treatments (CAMS and TAU), leaving $N=240$ participants eligible for Stage 2 treatments. Treatment responders at the end of Stage 1 will end study treatment and enter maintenance, which includes monthly monitoring and continued assessments with the IEs. All student participants will complete weekly measures as part of treatment. Research assessments by independent evaluators (IEs) will be conducted at baseline, mid-Stage 1 (Week 3), end of Stage 1 (Week 6), mid-Stage 2 (Week 10), end of Stage 2 (Week 14), and at 3-month follow-up (Week 26).

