Stage 2 analyses within Aim 8 focus on statistical contrast of the two randomized arms within Stage 2. Patients are the non-responders from Stage 1. Linear mixed models¹⁶³ (LMM, also known as random effects or growth curve models), fit with SAS PROC MIXED will be used to analyze the longitudinal data. LMMs use all available measurements, allowing student participants to have an unequal number of observations and producing unbiased parameter estimates if unobserved values are missing at random. The analysis will fit a LMM with fixed effects for the intercept, time, group, and a group-by-time interaction term, where group is an indicator of stage-one treatment (CC-DBT vs. CAMS as referent). The LMM will also include random effects for the intercept and time and an unstructured within-person correlation structure for the residual errors and will adjust for the following measures collected at baseline (pre-randomization): site, age, race, and clinical severity. Model diagnostics will be used to determine suitability of more parsimonious (e.g., autoregressive) correlation structures, and nonlinear (e.g., quadratic) effects for time. Complexity of the model and variance/covariance structures may be constrained by the available repeated measures. Counselor will be treated as a random effect which models potential correlation between student participants within a common counselor. If there is not sufficient variance, indicated by the reliability estimate of the random effect falling below 0.02 (a slighter lower threshold compared to Raudenbush and Bryk¹⁶⁴ (p.125), we will treat counselor as a fixed effect. The primary contrast is between groups' difference in change from Stage 2 randomization to end of Stage 2. Comparison of these findings will be to the results from the linear contrasts of the components of the ATS as described in Aim 1.

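### Aim 8 asks about CC-DBT versus continued CAMS in Stage 2, but its model compares CC-DBT with continued and first-time CAMS combined

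*Combined protocol and SAP*

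**What the plan says.** Section 3, Table 2, lists Aim 8 among the tertiary/exploratory aims. Its Stage 2 part asks "whether CC-DBT produces greater reductions in SR than Continued CAMS (Stage 2". Table 8 (Section 9.2) gives this comparator a specific place. Cell B is the CAMS non-responders who continue CAMS, and cell E is the TAU non-responders who switch to CAMS. Cells C and F are the corresponding switches to CC-DBT.

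Section 9.3.7 describes the analysis: "Stage 2 analyses within Aim 8 focus on statistical contrast of the two randomized arms within Stage 2". The population is not restricted by Stage 1 treatment: "Patients are the non-responders from Stage 1". The group term is described in these words: "where group is an indicator of stage-one treatment (CC-DBT vs. CAMS as referent". The listed baseline adjustments are "site, age, race, and clinical severity". The primary contrast is change from Stage 2 randomization to the end of Stage 2, and the findings are to be set beside the Aim 1 linear contrasts of strategy components.

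Section 4.2 defines the Stage 2 options as "1) CAMS (either continued or for the first time) or 2) CC-DBT". Where the plan means the combined CAMS arm elsewhere, it says so: Hypothesis 3 in Table 2 and the Aim 3 analysis in Section 9.3.2 both refer to CAMS as either added (or switched to) or continued.

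**The concern.** The objective and the model define two different comparisons. The objective, read with Table 8, is C vs B: among students who did not respond to CAMS, does switching to CC-DBT do better than staying on CAMS? The model pools over Stage 1 treatment and gives C+F vs B+E. Its comparator combines students continuing a treatment they have not responded to with students starting CAMS after TAU.

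Two things follow. The Stage 2 part of Aim 8 uses the same cells as Aim 3, although the two sections describe the time window differently, and the question Aim 8 states has no named analysis. And if the effect of CC-DBT depends on what came first, the pooled figure should not carry the label CC-DBT versus continued CAMS. Continue or switch is the decision a counseling center faces once CAMS has not worked, so the label matters to the reader.

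**Working it through.** **Inputs.** N = 480, 50% response and SSI SD 7 (Sections 4.2 and 9.2, the SD under Aim 2). Stage 1 attrition among non-responders of 25%, within-person correlation 0.60, Type I error 2.5%, and a difference of 3.4 points labelled d = 0.34 (Section 9.2, Aim 3).

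**Counts.** 480 × 0.5 = 240 non-responders; 240 × 0.75 = 180 re-randomized; 180 / 4 = 45 per cell; 2 × 45 = 90 per pooled arm. These match the plan. First-time CAMS is 45 of 90, or 50%, of the CAMS arm. Stage 1 treatment is not among the Stage 2 balancing factors in Section 6.3, so the realized share may differ.

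**The plan's nearest power figure.** None is given for Aim 8. For the pooled contrast under Aim 3 it claims over 80% at 90 vs 90.
- d = 0.34 with baseline adjustment (SD multiplier √(1 − 0.60²) = 0.8): 72.9% at two-sided 2.5%, 81.4% at one-sided 2.5%. The latter matches the claim.
- 3.4 points with SD 7, two-sided 2.5%: 84.5% unadjusted, 91.9% on change scores, 96.6% with baseline adjustment.
- The label d = 0.34 implies SD 3.4 / 0.34 = 10, not 7. That is a separate matter, so both are carried below.

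**What the pooled contrast estimates.** With equal cells it is (δ_CAMS-first + δ_TAU-first) / 2. The effects below are assumed for illustration:

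| CC-DBT minus continued CAMS (C vs B) | CC-DBT minus first-time CAMS (F vs E) | Pooled |
|---|---|---|
| 3.4 | 3.4 | 3.4 |
| 3.4 | 1.7 | 2.55 |
| 3.4 | 0 | 1.7 |

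On the d scale, 0.34 with 0.34, 0.17 or 0 gives pooled 0.34, 0.255 or 0.17. Pooled power is then 72.9%, 45.9% or 20.7% (baseline-adjusted, two-sided 2.5%). With equal effects, pooling distorts nothing.

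**Precision (SD 7, unadjusted).**
- Pooled: 7 × √(2/90) = 1.04
- C vs B: 7 × √(2/45) = 1.48
- Interaction, (C − B) − (F − E): 7 × √(4/45) = 2.09

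Baseline adjustment at correlation 0.60 multiplies each by 0.8, giving 0.83, 1.18 and 1.67. SD 10 unadjusted gives 1.49, 2.11 and 2.98. The ratios to the pooled standard error stay at 1.41 and 2.

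**Power for C vs B at 45 vs 45.**
- d = 0.34, baseline-adjusted: 41.1% (two-sided 2.5%) or 52.2% (one-sided 2.5%).
- 3.4 points with SD 7, two-sided 2.5%: 52.5% unadjusted to 73.8% baseline-adjusted.
- The interaction needs d of about 0.74 (baseline-adjusted) to 0.92 (unadjusted) for 80% power at two-sided 2.5%.

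**What Aim 1 already holds.** ATS-1 and ATS-2 share the responders in cell A. Their difference is about the non-response fraction times (C − B), which is 0.5 × (C − B) at 50% response. A 3.4-point difference between C and B would appear as about 1.7.

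**The case against.** The simplest defense is a slip of wording. Aim 8 opens by saying it works within each treatment stage, Section 9.3.7 speaks of the two randomized arms, and the model's label is plain CAMS. On that reading the analysis is as intended and one phrase in Table 2 is too narrow. The documents do not settle which is meant, so rewording must be an accepted answer. What stands is that the two texts disagree, and that the plan uses broader wording where it means the broader arm.

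Aim 1 is a second defense. It compares the four strategies separately, adds linear contrasts of their components, and Section 9.3.7 points back to them. One might infer that the ATS-1 versus ATS-2 contrast is too diluted to help. That is not so: the effect and its standard error shrink by about the same factor, so the contrast is rescaled and the information is kept. The gap is narrower. No component contrast is named as the answer to Aim 8, and a whole-strategy comparison does not use change from Stage 2 randomization.

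A reader might also infer that the model hides any carry-over from Stage 1. Re-randomization means a Stage 1 effect common to both Stage 2 arms cancels; only a Stage 1 by Stage 2 interaction is averaged. Nor does the Background promise that this model will show sequence effects. Its example, "that clients are satisfied with CC-DBT after CAMS, but not after TAU (or vice-versa", concerns satisfaction, and the remark on differential effects describes the whole design.

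**Conclusion.** The mismatch is real and sits in the current text: Aim 8 states C vs B and its Stage 2 model estimates C+F vs B+E. About half of the CAMS arm, 45 of 90 on the plan's assumptions, is not continued CAMS. How far the pooled result departs from the stated comparison depends on an interaction that the documents do not quantify. The departure is nil if the two effects are equal. It is half the C vs B effect if CC-DBT has no advantage over first-time CAMS; that case is assumed, not predicted.

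This is a defect of estimand and label in an exploratory aim. The documents do not support reading it as bias: randomization keeps the pooled contrast valid for the mixture, and no power claim or primary conclusion rests on Aim 8. Nor do they say that the result will be published as CC-DBT versus continued CAMS; the point is that the present wording invites it.

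**What to change.** In Section 9.3.7 (Aim 8, Stage 2), add Stage 1 treatment and its interaction with Stage 2 treatment and time, including the lower-order terms. Name C vs B as the contrast for continued CAMS, report F vs E beside it as CC-DBT versus first-time CAMS, and give both as estimates with intervals. Keep the pooled C+F vs B+E contrast under Aim 3.

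If the pooled arm was intended, reword Aim 8 in Table 2 so that the comparator is CAMS, continued or first-time, and accept that it then largely duplicates Aim 3.

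In either case, correct the description of the group term in Section 9.3.7, where an indicator coded "CC-DBT vs. CAMS as referent" is called stage-one treatment; it is Stage 2 treatment.

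No new data are needed. The cost is precision and some model complexity, which Section 9.3.7 already warns may be limited by the available repeated measures. With about 45 per cell, the standard error for C vs B is about 1.4 times the pooled one and that for the interaction about twice. The interaction test will have low power and should not decide whether the two contrasts are shown. That is acceptable for an exploratory aim.

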4 STUDY DESIGN

4.1 THE STUDY TEAMS(S)

Student participants: Students who meet all inclusion and no exclusion criteria and provide consent.

Counselor participants: CCC counselors who meet all inclusion and no exclusion criteria and provide consent.

Intake counselor: CCC counselor who meets all new students seeking mental health services.

Study liaison: Research staff, employed by the CCC, who are responsible for acting as a liaison between the CCC and study. Duties may include exporting study data from the electronic medical record, conducting consent visits, facilitating participant recruitment and treatment, and meeting with potential student participants and counselor participants.

Independent Evaluator (IE): Research staff responsible for conducting all baseline and longitudinal assessments.

Project Coordinator (PC): Site research staff responsible for day-to-day operations of the study.

4.2 OVERALL DESIGN

As shown in Figure 1 (on page 9), the proposed multisite SMART will involve randomization at two stages. At Stage 1, all student participants ($N = 480$) will be randomized to 4-6 weeks of CAMS or TAU. Beginning at session 4, the counselor will rate the student participant in terms of clinical response. Insufficient responders (e.g., non-responders) to Stage 1 will be re-randomized to one of two Stage 2 treatments for an additional 1-8 weeks: 1) CAMS (either continued or for the first time) or 2) CC-DBT.

Thus, four ATSSs are possible:

- ATS-1: Start with CAMS, if responding, enter maintenance treatment; if not, continue with CAMS;
- ATS-2: Start with CAMS, if responding, enter maintenance treatment; if not, switch to CC-DBT;
- ATS-3: Start with TAU, if responding, enter maintenance treatment; if not, switch to CAMS;
- ATS-4: Start with TAU, if responding, enter maintenance treatment; if not, switch to CC-DBT.

Our pilot showed at Stage 1, 48% and 44% treatment response rates across CAMS and TAU, with 27% and 17% attrition rates, respectively—differences not statistically significant. Based on these findings, we assume an equal response rate of 50% across both Stage 1 treatments (CAMS and TAU), leaving $N=240$ participants eligible for Stage 2 treatments. Treatment responders at the end of Stage 1 will end study treatment and enter maintenance, which includes monthly monitoring and continued assessments with the IEs. All student participants will complete weekly measures as part of treatment. Research assessments by independent evaluators (IEs) will be conducted at baseline, mid-Stage 1 (Week 3), end of Stage 1 (Week 6), mid-Stage 2 (Week 10), end of Stage 2 (Week 14), and at 3-month follow-up (Week 26).

4.3 SCIENTIFIC RATIONALE FOR STUDY DESIGN

SMART designs provide a rigorous and principled approach to constructing decision rules that guide adaptive interventions, including type, dosage, sequence, and response to treatment.¹⁷ ATSSs are recommended when patients vary in response to treatment, the effectiveness of an intervention changes over time due to waxing and waning of symptoms, comorbidity renders

treatment more complex, there is a high probability of relapse, and adherence to interventions is difficult to achieve.¹⁷ All of these conditions apply when treating SR at CCCs. Also, ATSSs may help bridge the critical gap between research and practice,¹⁷ as ATSSs mirror more closely what happens in the real world (e.g., if one treatment does not work, try another). In addition, the lengths of treatment for our stages (4-6 weeks for Stage 1 and up to 8 weeks for Stage 2) were chosen in order to best match practices of CCCs (where average number of sessions is 5-6) and therefore are most likely to be implemented.

4.4 JUSTIFICATION FOR INTERVENTION

First Stage (Stage 1) of SMART Study (N=480): Randomization to TAU or CAMS (4-6 Weeks). After baseline, student participants will be randomly assigned to TAU (n= 240) or CAMS (n=240). Stage 1 treatment will last 4-6 weeks. We chose this treatment length because the average number of sessions at CCCs is 5.22 (with a median of 4 sessions),²¹ 6-8 CAMS sessions were enough to resolve SR in college students in an earlier trial,²⁷ and in our CAMPUS feasibility study, average number of Stage 1 sessions was 6. Student participants who appear to be deteriorating (worsening SI on the Counselor CGI-I scale) or who maintain high levels of SI without improvement may be re-randomized to Stage 2 early after session 4.

Student participants randomly assigned to TAU will receive the customary treatment they would receive at that CCC—on average, weekly individual therapy, but it may also occasionally include group participation and/or medication referral. Counselors conducting TAU treatment will be informed to do counseling as usual for a period of 4-6 weeks, except that counselors will be asked not to utilize CAMS or DBT strategies. The book entitled *“Collaborative Assessment and Management of Suicidality: Managing Suicidal Risk: A Collaborative Approach (2nd edition)”*⁷ will serve as the manual for CAMS treatment in Stage 1/Stage 2. CAMS individual sessions will be provided weekly for 50-60 minutes and will follow the Suicide Status Form.

Second Stage (Stage 2) of SMART Study (n≈240): Re-randomization to CC-DBT or CAMS (1-8 Weeks). The treatment length for Stage 2 was chosen based on previous studies with CAMS and DBT, ease of dissemination to CCCs later, and informed by data from the CAMPUS feasibility study. Based on previous CAMS studies,²⁷ our pilot study and CAMPUS feasibility study, we estimate that n≈240 of student participants will resolve their SR during Stage 1 and that n≈240 will be re-randomized to Stage 2.

DBT Individual Therapy. Participants will receive weekly individual teletherapy/in-person sessions with a CC-DBT-trained counselor for up to 8 weeks total. The DBT manual²⁹ guidelines such as orienting clients to the treatment model, using a diary card to monitor problematic behaviors, relying on a hierarchy of targets to guide treatment at each session, and conducting chain and solution analyses to determine and address controlling variables of problematic behavior will be followed.¹⁴⁵

DBT Skills Training. The skills training sessions will follow the DBT Skills Training manual,^{8,29,144} but adapted to fit within a standard academic term (6 weeks). The skills training sessions will be provided via teletherapy/in person and will include skills from all four modules of skills acquisition (mindfulness, emotion regulation, interpersonal effectiveness, and distress tolerance), but with the following modifications: greater focus on emotion regulation given past research with college students,^{12,146} and fewer skills taught within each module. Depending on participant flow and time of the semester/quarter, skills training may be conducted individually or in group format.

Peer consultation team is an inherent part of DBT. Counselors will participate in weekly DBT consultation team meetings conducted remotely or in person.^{29,147} Phone/text skills coaching is viewed as essential for the generalization of DBT skills to the environment.²⁹ Counselors will coach their own student participants but, adapting to this setting, they will be encouraged to observe their own limits and comply with local CCC policies/legal requirements, as warranted.

Hybrid Intervention Model

For the purposes of these studies, hybrid intervention model means that a student participant's course of treatment may be delivered completely via telehealth, completely in person, or via a combination of in-person and telehealth sessions. Decisions about what type of sessions to hold will be made by the counselor and based on several factors, including university and CCC policy, location/preference of the student participant, and location/preference of the counselor participant. We will be collecting data on the number of sessions conducted via each modality (captured via Titanium, the electronic medical record [EMR] utilized by all sites) as well as the number of participants who receive just teletherapy, just in-person sessions, and a combination. We recognize that allowing the modality of treatment delivery to vary between- and within-subjects may contribute to greater variability. We considered alternative treatment designs (e.g., constraining the treatment delivery to telehealth only) to reduce this variability. However, we decided to allow for flexibility in treatment delivery for several reasons. First, because this variability in delivery mode will occur across all arms, irrespective of treatment type, we do not expect it to bias the outcome analyses. Second, we do not believe constraining modality is reflective of the reality of practice in CCCs going forward (i.e., beyond the immediate response to Covid-19). Thus, we believe constraining the treatment modality in the study design would limit the external validity of the trial results. Third, relatedly, we believe a hybrid model has the greatest dissemination and implementation potential in the future across CCCs, where the expectation is that delivery of treatment will continue to vary within and across settings and will likely be some combination of in person and remote sessions. Thus, the resulting sequencing of care allows for this flexibility by design.

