Notes (2): \$For all assessments collected as part of an Independent Evaluator (IE) visit (i.e., those assessments not collected specifically at treatment visits), there will be a +/-1 week window around the scheduled assessment date for purposes of data collection. IE assessments collected outside of this window will still be collected and values will be imputed based on when the assessment should have occurred.																
Notes (3): *These measures are exclusively collected in the Titanium electronic medical record and will be exported at regular intervals throughout the study period.																

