Management of College Session Breaks. CAMS and CC-DBT individual sessions will be conducted either in-person or remotely via a HIPAA-compliant telehealth platform. Thus, management of treatment during short breaks will not be difficult. The end of an academic term often serves as a natural and longer-term break in treatment in CCCs. Given the nature of the academic calendar, participants may take a “break” from the study treatment while they are on academic breaks if they are unable or ineligible to receive CCC services (e.g., residing out of state for the summer), and then continue where they left off upon return. This is an essential adaptation to the setting, and it has been considered in terms of recruitment rates and will also

be considered in the analyses (e.g., dosage defined as number of sessions and not time since randomization per stage; number of additional treatment sessions received).

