Aim 2 analyses will contrast ATSSs beginning with CAMS vs. interventions beginning with TAU (i.e., to evaluate the main effect of initial treatment) on change (decrease) in suicide-related risk behaviors (SI, NSSI, and suicide attempts—the primary outcomes) from baseline to the end of Stage 2 (the primary contrast). This is a comparison of cells A+B+C vs. D+E+F (see Figure 2 and Table 8). Note that the primary continuous longitudinal outcome is assessed at baseline, mid-Stage 1 (3 weeks), post Stage 1 (6 weeks), mid-Stage 2 (10 weeks), post-Stage 2 (14 weeks) (end of acute treatment) and then again at 3-month follow-up (26 weeks), for a total of 6 measurement occasions. Linear mixed models¹⁶³ (LMM, also known as random effects or growth curve models), fit with SAS PROC MIXED will be used to analyze the longitudinal data. LMMs use all available measurements, allowing student participants to have an unequal number of observations and producing unbiased parameter estimates as long as unobserved values are missing at random. The analysis will fit a LMM with fixed effects for the intercept, time, group, and a group-by-time interaction term, where group is an indicator of phase-one treatment (CAMS vs. TAU as referent). The LMM will also include random effects for the intercept and time and an unstructured within-person correlation structure for the residual errors and will adjust for the following measures collected at baseline (pre-randomization): site, age, race, and clinical severity. Model diagnostics will be used to determine suitability of more parsimonious (e.g., autoregressive) correlation structures, and nonlinear (e.g., quadratic) effects for time. We do not expect the intervention effects to be attenuated due to counselor participants who are cross classified between the interventions. Nonetheless, we will assess the potential attenuation by assessing the counselor x intervention interaction. If significant, we will examine if the attenuation effect is limited to a select few counselors and eliminate as needed to remove potential counselor contamination of intervention effects. Counselor will be treated as a random effect which models potential correlation between student participants within a common counselor. If there is not sufficient variance, indicated by the reliability estimate of the random effect falling below 0.02 (a slighter lower threshold compared to

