Aim 8 analyses focus on statistical contrast of the two randomized arms within Stage 1 and the two randomized arms within Stage 2. For Stage 1 comparisons, linear mixed models¹⁶³ (LMM, also known as random effects or growth curve models), fit with SAS PROC MIXED will be used to analyze the longitudinal data. LMMs use all available measurements, allowing student participants to have an unequal number of observations and producing unbiased parameter estimates if unobserved values are missing at random. The analysis will fit a LMM with fixed effects for the intercept, time, group, and a group-by-time interaction term, where group is an indicator of stage-one treatment (CAMS vs. TAU as referent). The LMM will also include random effects for the intercept and time and an unstructured within-person correlation structure for the residual errors and will adjust for the following measures collected at baseline (pre-randomization): site, age, race, and clinical severity. Model diagnostics will be used to determine suitability of more parsimonious (e.g., autoregressive) correlation structures, and nonlinear (e.g., quadratic) effects for time. Complexity of the model may be constrained by the available repeated measures. Counselor will be treated as a random effect which models potential correlation between student participants within a common counselor. If there is not sufficient variance, indicated by the reliability estimate of the random effect falling below 0.02 (a slighter lower threshold compared to Raudenbush and Bryk¹⁶⁴ (p.125), we will treat counselor as a fixed effect. The primary contrast is between groups’ difference in change from baseline to end of Stage 1. Comparison of these findings will be to the results from the linear contrasts of the components of the ATS as described in Aim 1.

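### For students re-randomised before Week 6, the end-of-Stage-1 evaluator score usually comes after the Stage 2 assignment, and the plan names no Stage 2 starting value for them.

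*Combined protocol and SAP*

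**What the plan says.** Section 4.2 sets the evaluator visits after baseline at "mid-Stage 1 (Week 3), end of Stage 1 (Week 6), mid-Stage 2 (Week 10), end of Stage 2 (Week 14"), with a last visit at Week 26. Section 9.3.2 carries the same week values into the longitudinal model. Table 1, Notes (2), adds that "there will be a +/-1 week window around the scheduled assessment date"; scores from outside the window are kept but imputed to the scheduled time.

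Stage 1 lasts 4 to 6 weeks. Section 4.4 says that students who are worsening or "who maintain high levels of SI without improvement may be re-randomized to Stage 2 early after session 4". Section 8.1 allows significantly worsening students to be re-randomised earlier, and that sentence states no minimum session. At the second randomisation, section 6.3 has the coordinator collect the blocking variables and the tailoring variable. It mentions no evaluator assessment.

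Section 9.3.7 (Aim 8) takes as its Stage 1 contrast the "difference in change from baseline to end of Stage 1" and as its Stage 2 contrast the "difference in change from Stage 2 randomization to end of Stage 2". It does not say which visit supplies either value when re-randomisation comes before Week 6.

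**The concern.** The stages follow treatment progress and the evaluator visits follow the week number. Between Week 3 and Week 10 the only evaluator score is the one labelled end of Stage 1. For a student re-randomised early, that score may be taken when Stage 2 treatment is already under way.

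Two things are at stake:

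- **Stage 2.** A starting value measured after randomisation absorbs part of the CC-DBT versus CAMS difference, so change from Stage 2 randomisation is understated.
- **Stage 1.** Some students scored as TAU outcomes would already be receiving CAMS or CC-DBT. If those treatments do better than TAU, as the trial hypothesises, CAMS versus TAU at the end of Stage 1 moves toward no difference. The synopsis lists that time point under the primary endpoint.

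The affected students are selected for worsening or lack of improvement, so the error is not random noise.

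**Working it through.** The plan gives no figure on this point to reproduce. The check is one of dates.

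**Inputs**

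- Baseline is day 0, and weeks are counted from it (assumption). The first session is typically within 7 days (6.1.3), so s = day 1 to 7.
- Stage 1 sessions are weekly for up to 6 weeks (6.1.6).
- Week 6 visit: 6 x 7 = 42, +/-7, so day 35 to 49 (4.2; Table 1, Notes (2)).
- Assumptions: re-randomisation falls on the day of session k after m missed weeks, and the first Stage 2 session is one week later.

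**Timing.** Re-randomisation day = s + 7(k - 1 + m). Lag = visit day - re-randomisation day. Stage 2 sessions held = whole weeks in the lag.

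| k + m | Re-randomised on day | Lag, visit day 35 | Lag, visit day 42 | Lag, visit day 49 |
|---|---|---|---|---|
| 4 | 22-28 | 7-13 (1 session) | 14-20 (2) | 21-27 (3) |
| 5 | 29-35 | 0-6 (0) | 7-13 (1) | 14-20 (2) |
| 6 | 36-42 | -7 to -1 | 0-6 (0) | 7-13 (1) |
| 7 | 43-49 | -14 to -8 | -7 to -1 | 0-6 (0) |

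After session 4 with none missed, the in-window visit is always late, by 7 to 27 days. After session 5, or session 4 with one missed week, a day-42 visit is 7 to 13 days late. After session 6, or session 4 with two missed weeks, a day-42 visit comes before the first Stage 2 session.

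The SSI looks back two weeks (8.1). A day-42 score covers days 28 to 42, none of it before a re-randomisation on day 22 to 28.

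**Size in Stage 2, per affected student.** Assume the 3.4-point difference in section 9.2 (Aim 3) builds linearly over 8 weeks (56 days) from the first Stage 2 session. Each week is 1/8 = 12.5%, or 3.4/8 = 0.425 points. For re-randomisation after session 4 with none missed, the first Stage 2 session is on day 29 to 35:

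- Visit on day 42: exposure 7 to 13 days; 7/56 = 12.5% (0.43 points) to 13/56 = 23.2% (0.79 points).
- Largest in-window exposure: 49 - 29 = 20 days; 20/56 = 35.7% (1.21 points).

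**Reach in Stage 1.** Let f be the share of non-responders re-randomised early enough to be affected; the documents do not give it. Section 4.2 expects 240 non-responders, 120 per arm. Every affected TAU student has left TAU: 120f/240. About half of the affected CAMS students change treatment, to CC-DBT: 60f/240.

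| f | Affected, of 480 | TAU arm off TAU | CAMS arm off CAMS |
|---|---|---|---|
| 10% | 24 | 5% | 2.5% |
| 25% | 60 | 12.5% | 6.25% |
| 50% | 120 | 25% | 12.5% |
| 100% | 240 | 50% | 25% |

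If 180 are re-randomised (section 9.2, after 25% attrition), all these figures are multiplied by 0.75.

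**The case against.** Early re-randomisation is permitted, not prescribed. A fixed Week 6 visit is also a sound choice for comparing the Stage 1 arms: everyone is measured at a common time, by intention to treat. Moving the visit forward for non-responders only would make its timing depend on a post-randomisation outcome and lose that comparison. This stands, and it is why the remedy below leaves the schedule alone. It does not rescue a Stage 2 starting value measured after Stage 2 randomisation.

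A reader might infer more than the documents support:

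- **That all non-responders are affected.** Those re-randomised after session 6 are largely unaffected. Section 4.4 reports an average of 6 Stage 1 sessions in the feasibility study, but Stage 1 there allowed up to 8, so the figure does not settle the early share here.
- **That the main results are compromised.** Aim 1 is analysed at 14 weeks, and Aim 2's main contrast runs from baseline to the end of Stage 2. Neither uses Week 6 as endpoint or starting value. Aim 8 is exploratory.
- **That Week 3 is always a clean starting value.** Its window is day 14 to 28 and session 4 falls on day 22 to 28, so it need not come first.
- **That visits run on through term breaks and reach students with Stage 1 unfinished.** The synopsis counts treatment in academic weeks, and section 6.1.6 says "dosage defined as number of sessions and not time since randomization per stage". No text says that the evaluator clock continues through a break.

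Use of the Week 6 score as the Stage 2 starting value is itself an inference. Section 9.3.7 names the event but no visit, and section 9.3.3 (Aim 4) speaks only of baseline, midpoints and endpoints. The week 4 to week 24 span given for Aim 3 in section 9.3.2 matches no evaluator schedule and does not resolve it.

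**Conclusion.** The point holds for students re-randomised after session 4 or 5 with few missed sessions. For them the plan either has no defined starting value at Stage 2 randomisation or, if scores are slotted to nominal weeks, uses one that is usually taken after assignment. This bears on both Aim 8 contrasts and probably on Aim 3 and the Stage 2 part of Aim 4. The Stage 1 dilution is heavier in the TAU arm.

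The loss of about 12.5% per week of prior exposure applies to an affected student and rests on linear build-up; faster early gains would raise it. It also ignores the SSI look-back, which can carry pre-treatment days into the score and reduce the loss. No trial-wide average can be stated without the early share.

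**What to change.** Change the analysis text, not the visit schedule or the re-randomisation rule.

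1. In Aims 3 and 8 and the Stage 2 part of Aim 4 (9.3.2, 9.3.3, 9.3.7), define the Stage 2 starting value as the last evaluator score obtained before the Stage 2 assignment is revealed.
2. In those analyses, enter evaluator scores at their actual dates relative to re-randomisation, and amend Table 1, Notes (2), so that they are not imputed to the scheduled week.
3. In the Aim 8 Stage 1 contrast, flag scores taken after the reveal. Keep the fixed Week 6 comparison as the common-time intention-to-treat result, and add a sensitivity analysis in which flagged scores do not count as Stage 1 outcomes.
4. Report the number re-randomised before their Week 6 visit, by Stage 1 arm.
5. Reconcile sections 4.4 and 8.1 on how early re-randomisation may occur.

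The cost is wording, plus keeping the reveal date and each assessment date in the analysis file. No visit is added and Stage 2 is not delayed. The downside is that some early students will have Week 3 as their starting value, which is older and noisier. In the sensitivity analysis, the students whose scores are set aside are selected for poor response, so it supports the fixed-time result and does not replace it.
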